### **f) Study Endpoints**

Primary study endpoints are average VAS pain score during hospitalization and postoperative narcotic usage during the hospitalization. Secondary endpoints are need for antiemetic therapy, length of hospitalization, and aggregate pain and quality of

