## Enhanced pain control after reduction mammoplasty with bupivacaine and dexamethasone regional block

### 1) Abstract of the study

**Background:** Patients undergoing reduction mammoplasty frequently suffer significant post procedure pain at the operative site. While regional nerve block is routinely performed with bupivacaine, the effects of this are limited to the up to 8 hours of action provided by this drug. Previous studies in orthopedic and thoracic surgery patients have demonstrated that addition of dexamethasone to the perineural block prolongs the duration of analgesia. This has never been studied in the plastic surgery patient. We propose that addition of dexamethasone to the infiltration solution will prolong the duration of analgesia provided by a regional block and reduce the need for adjunct narcotic medication in the postoperative period following reduction mammoplasty.

**Methods:** Patients undergoing elective Breast Surgery at Temple University Hospital will be randomized to receive a control standard perineural block with 19-mL 0.5% bupivacaine +1mL 0.9% sterile saline or block with the experimental mixture of 19mL 0.5% bupivacaine + 1mL 4mg/mL dexamethasone solution for each breast. Primary end points will be mean pain VAS score as measured every 4 hours postoperatively and postoperative narcotic consumption data during the admission following the procedure. Secondary endpoints also observed will be anti-emetic consumption, vital signs, quality of life as assessed by SF-36 and Breast-Q questionnaires, and length of hospital stay.

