### 5) Objectives

This study aims to evaluate the effect of the addition of dexamethasone to a standard bupivacaine nerve block following reduction mammoplasty. We propose that addition of dexamethasone to the infiltration solution will prolong the duration of analgesia provided by a regional block and reduce the need for adjunct narcotic medication in the postoperative period following reduction mammoplasty.

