### **g) Procedures Involved in the Human Research**

Study subjects will undergo breast surgery by the individual surgeon's standard technique. No changes in surgical technique will occur as part of this study. Regional nerve block with bupivacaine and/or lidocaine is typically offered to patients as part of this procedure and is considered standard of care. However, not all patients opt to receive a nerve block

For the study, subjects will be randomized to experimental and control groups in a ratio of 1:1. Randomization will occur upon enrollment in the study. When the patient is enrolled, the investigator will use the Sealed Envelope™ simple randomization tool to assign the subject a treatment group. Randomization occurs in random permuted blocks to achieve an even distribution between groups. Patients will be blinded to their study group.

All subjects will receive perineural nerve block in the preoperative holding area prior to the case performed by faculty from the anesthesia pain service. An ultrasound guided pecs block will be performed. For the block, the fascial plane separating the pectoralis major and pectoralis minor muscles is identified by ultrasound at the level of the 3rd rib. A needle is advanced into this space and the local anesthetic is infiltrated. The experimental group will receive 29cc 0.5% bupivacaine mixed with 1mL 4mg/mL dexamethasone for each side (40 cc total). The control group will receive 29cc 0.5% bupivacaine mixed with 1mL 0.9% saline solution for each side.

All patients will undergo standard breast reduction with no change in the standard operative technique.

All patients will receive a standard postoperative pain regimen as follows:

- Percocet 5/325 1 tab q4hr prn pain (moderate, 4 – 7)
- Percocet 5/325 2 tabs q4hr prn pain (severe, 8 – 10)
- IV 1mg Morphine q1hr prn breakthrough pain
- IV 4mg Zofran q8hrs prn N/V

This may be adjusted for patient drug allergies

Bupivacaine is a local analgesic used routinely during surgical procedures. It is FDA approved for this indication.

Dexamethasone is a glucocorticoid available in oral and intravenous formulations. It is FDA approved for a multitude of anti-inflammatory indications. While off label, it is standard of care to provide IV

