## Enhanced pain control after reduction mammoplasty with bupivacaine and dexamethasone regional block

Data will be extracted from the Epic electronic medical record. Consultation with medical informatics has been obtained to assist with development of an automated data collection mechanism. Data will be stored in a spreadsheet that allows for manipulation and analysis. Patient surveys will be conducted a week after the procedure and documented on paper and the responses will be manually inputted into an electronic database (REDCap). Survey responses (REDCap) will be matched to inpatient data measurements (Epic) through study ID numbers. The spreadsheet itself will be encrypted and will be stored exclusively on hospital network databases.

The two groups will be compared using a Student T test to evaluate for significant differences in the endpoints of each group.

A 2 mean 2 sided power analysis was conducted assuming the mean VAS difference between groups to be 1.5. A sample size of 30 in each group will have 81% power to detect a difference in means of 1.500 assuming that the common standard deviation is 2.000 using a two group t-test with a 0.050 two-sided significance level. We anticipate using larger numbers to power subgroup analysis.

Analysis between the two groups will involve a linear mixed effect model to compare the pain scales of the two groups over time. If vital signs are dissimilar at the beginning of the study, they will be controlled for prior to analysis. Pain medication requirement (determined by quantity of pills or mg used of same medication) will also be controlled within the analysis model. Adjustments to the pain score within the groups due to pain medication usage will be performed.

However, need for postoperative anti-emetic therapy is expected to be a somewhat rare event with similar means. In a similar power analysis with an expected group A mean of 0.5 doses and group B mean of 1 dose with standard deviation of 1, a sample size of 63 is required to reach significance. A somewhat large standard deviation is expected given the need for repeated dosing in those who do experience post-operative nausea

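### The VAS mixed model controls for narcotic use, the other primary endpoint, so it does not estimate the difference behind the 81% power; neither the decisive VAS analysis nor a success rule for the two primaries is stated

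*Combined protocol and SAP*

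**What the plan says.** - **Endpoints.** Section 10(f): "Primary study endpoints are average VAS pain score during hospitalization and postoperative narcotic usage during the hospitalization". The Abstract names the same pair: "Primary end points will be mean pain VAS score as measured every 4 hours postoperatively and postoperative narcotic consumption data during the admission". Neither place ranks them.
- **Hypothesis.** Section 5 expects the treatment to "prolong the duration of analgesia provided by a regional block and reduce the need for adjunct narcotic medication".
- **How narcotics are given.** In section 10(g) the as-needed orders are tied to the pain score. The order for moderate pain begins "Percocet 5/325 1 tab q4hr prn pain (moderate, 4 – 7", and two tablets are ordered for scores 8 to 10. Intravenous morphine covers breakthrough pain.
- **Analysis.** Section 10(i) first says: "The two groups will be compared using a Student T test to evaluate for significant differences in the endpoints of each group". It then gives 81% power with 30 per group for a VAS difference of 1.5 (SD 2.0, two-group t-test, two-sided 0.05). After that it adds: "Analysis between the two groups will involve a linear mixed effect model to compare the pain scales of the two groups over time". On narcotics it says: "Pain medication requirement (determined by quantity of pills or mg used of same medication) will also be controlled within the analysis model", and also: "Adjustments to the pain score within the groups due to pain medication usage will be performed".
- **What is not stated.** The plan does not say which VAS analysis decides, how the pain scores are to be adjusted, or whether medication enters the model as a patient total or a time-varying dose. It gives no testing order, alpha split or either/both rule for the two primaries, and no power calculation for narcotic use.

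**The concern.** Narcotic use is an outcome of treatment, not a baseline covariate. Pain drives it, the treatment is meant to lower it, and it is itself a primary endpoint. Conditioning on it changes the question from how much VAS differs between arms to how much VAS differs between patients who used the same amount of narcotic. The two coincide only if treatment leaves narcotic use unchanged, contrary to the study's hypothesis, or if narcotic use is unrelated to VAS within arms, which score-triggered dosing makes unlikely.

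With both analyses in the plan and neither designated, the one that decides could be chosen after the data are seen. The adjusted one could hide a real VAS benefit, or show a VAS difference between arms whose mean VAS is the same. Separately, without a success rule for the two primaries, neither the error rate nor the power of the trial's overall conclusion is defined.

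**Working it through.** **1. The stated power.** Inputs from 10(i): difference 1.5, SD 2.0, 30 per group, two-sided 0.05. Noncentrality = 1.5 / (2 × √(2/30)) = 1.5 / 0.516 = 2.90 on 58 degrees of freedom. Power by the noncentral t is 81.5%, so the 81% reproduces. It belongs to the unadjusted t-test.

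**2. What the adjusted model estimates.** The documents give no narcotic SD, narcotic effect or VAS–narcotic correlation, so these are assumptions. Let d be the reduction in narcotic use in SD units and r the within-arm patient-level correlation. The protocol does not fully specify its mixed model. As a stand-in I use ANCOVA of each patient's mean VAS on arm and narcotic total, with both outcomes bivariate normal.

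Expected adjusted difference = true difference − r × d × 2.

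Approximate variance of that contrast = 2² × (1 − r²) × [2/30 + (d² + 2/30)/58].

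Example with a true difference of 1.5, d = 0.5 and r = 0.3: the difference is 1.5 − 0.3 × 0.5 × 2 = 1.2. The variance is 4 × 0.91 × 0.0721 = 0.2625, so SE = 0.512. The ratio is 2.34, and power ≈ Φ(2.34 − 2.00) ≈ 63%. Simulation gives about 64%. Simulated power in all six settings:

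| Narcotic effect d | r | Adjusted difference | Power of adjusted test |
|---|---|---|---|
| 0.5 | 0.3 | 1.20 | about 64% |
| 0.5 | 0.5 | 1.00 | about 56% |
| 0.75 | 0.3 | 1.05 | about 50% |
| 0.75 | 0.5 | 0.75 | about 34% |
| 0 | 0.3 | 1.50 | about 85% |
| 0 | 0.5 | 1.50 | about 90% |

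The shift reverses if r is negative: at d = 0.5 and r = −0.3 the adjusted difference is 1.5 + 0.3 = 1.8.

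**3. Equal mean VAS.** The expected adjusted difference is then −r × d × 2. That is −0.3 or −0.5 at d = 0.5 (r = 0.3 or 0.5), and −0.45 or −0.75 at d = 0.75. The adjusted test is significant in 9% or 19% of trials at d = 0.5, and in 13% or 33% at d = 0.75. With positive r, the arm using less narcotic looks more painful; with negative r, less painful.

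**4. Two primaries, neither differing, two-sided 0.05 each.**
- Either counts: 1 − 0.95² = 9.75% at r = 0, falling to 7.0% at r = 0.9 (bivariate normal). If the adjusted VAS test is a further route to success, 10–11%.
- Both required: no inflation from the two t-tests.

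**5. Joint power if both are required, VAS difference 1.5.**
- Narcotic effect 0.75 SD: 0.815 × 0.815 = 66% at r = 0, rising to 77% at r = 0.9.
- Narcotic effect 0.5 SD: 0.815 × 0.478 = 39% at r = 0, rising to 48% at r = 0.9.

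**6. Both required, but the VAS analysis left open.** With equal mean VAS and a narcotic effect of 0.75 SD, the narcotic test plus either VAS test is significant in 13% (r = 0.3) or 29% (r = 0.5) of trials, counted two-sided. With positive r, most of these VAS results go against dexamethasone; with negative r the direction reverses.

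**The case against.** The strongest reply is that 10(i) already contains the right VAS analysis. Section 10(f) defines the endpoint as an average, 10(i) assigns the t-test to the endpoints, and VAS is powered by a t-test. The mixed model comes afterwards and concerns pain over time, so it may be meant only for the time course. This is a natural reading, and on it the 81% attaches to an analysis in the plan. What stands is that the plan does not say so, and that its one detailed description of the between-group VAS analysis is the narcotic-adjusted model.

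Second, the hypothesis in section 5 joins prolonged analgesia and lower narcotic use with a conjunction, which leans towards requiring both. That is fair, but an objective is not a success rule, and duration of analgesia is not mean VAS.

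Third, the power figures come from a stand-in model with assumed inputs, and as-needed doses are likely to be discrete and perhaps skewed. That is correct: the figures show possible size and are not predictions. The change of question does not depend on them.

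Fourth, 10(i) anticipates larger numbers for subgroup analysis, so power may exceed what 30 per group gives. Section 10(d) nevertheless plans about 60 in total, and more patients would not change what the adjusted model estimates.

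**Conclusion.** The main point holds. As written, the mixed model gives a VAS contrast at equal narcotic use, which is not the unadjusted 1.5-point difference behind the 81%, and the plan does not say that the t-test takes precedence. In the settings shown, the adjusted test has anywhere from 34% to 90% power for the same true VAS difference. That spread rests on assumed values of r (0.3 to 0.5) and d (0 to 0.75).

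The missing success rule is real but secondary. Its consequence depends on which rule the team intends.

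A reader might infer three stronger things that the documents do not support:
- **That the trial has a 7–10% false-positive rate.** This follows only if either endpoint counts, and no section says that it does.
- **That adjustment must shrink a benefit.** It can also enlarge it, or raise precision when narcotic use does not differ between arms.
- **That a significant adjusted result with equal mean VAS is an ordinary type I error.** If narcotic use truly differs, the model is testing another quantity, and that quantity is not zero.

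Requiring both endpoints does not by itself make an open choice of VAS analysis safe, as step 6 shows.

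**What to change.** **VAS analysis, section 10(i).** Name the unadjusted t-test on each patient's mean VAS as the decisive analysis. It is the one powered, and it matches the endpoint in 10(f). Use the mixed model's overall arm contrast, without narcotic adjustment, as a sensitivity analysis. Label the narcotic-adjusted model, and any adjustment of pain scores for medication, as supportive. Cost: wording only, plus the precision that adjustment would have gained had narcotic use not differed between arms (about 85% or 90% power instead of 81%).

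**Success rule, sections 10(f) and 10(i).** Test in fixed sequence, VAS then narcotic use, each at two-sided 0.05. This holds the error across the pair at 5% and keeps the 81% VAS power and 30 per group. Cost: no confirmatory narcotic claim if VAS fails. If narcotic use truly differed by 0.75 SD and VAS did not differ, such a claim would be made in only 3–4% of trials.

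If the team instead requires both endpoints, it should say so and replace the 81% with joint power, stating the narcotic effect, SD and correlation assumed. At 30 per group that is well below 81% if the narcotic effect is only 0.5 SD (step 5), so the sample size may need to be reconsidered under that rule.

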## Enhanced pain control after reduction mammoplasty with bupivacaine and dexamethasone regional block

life survey scores at the first post-operative visit. . Patient participation is concluded following the first post-operative visit

Patient participation will be terminated if any adverse reaction to the study medication is noted.

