### **e) Study Timelines**

- Data collection will occur over a period of 12 months
- [Interim analysis will be conducted by an independent at 6 months to confirm the quality of the data](#)
- Patient participation is limited to the length of the hospitalization for breast reduction procedure plus the first postoperative visit. For most subjects this will be 24 hours as inpatients with the postoperative visit occurring 1 week after surgery.

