## Enhanced pain control after reduction mammoplasty with bupivacaine and dexamethasone regional block

inadvertent systemic injection of the anesthetic. There is a very small risk of pneumothorax.

Primary additional risk to subjects compared to the standardly practiced block is allergic or adverse reaction to the study medication posed by the administration of dexamethasone. Adverse effects of this medication include behavioral disturbance, cardiac arrhythmia, hyperglycemia, and immune suppression. There is additional risk of increased postoperative pain due to deviation from standard nerve block procedure.

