### **13) Privacy and Confidentiality**

All PHI will be removed prior to storage of any patient information. PHI will not be shared with any research personnel or any other persons. Randomization status and all medications received will be disclosed to all healthcare personnel involved in the patient's care while in the hospital. The patient will not be informed of his or her study group. Patients will be completely informed of all privacy procedures as part of the consent process. Study personnel will be available to answer questions throughout the duration of the study.

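### Ending participation after any adverse reaction stops study observation once the block has been given, so outcome data can be lost unequally between arms and bias the comparison in either direction

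*Combined protocol and SAP*

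**What the plan says.** The rule stands at the end of section 10(f): "Patient participation will be terminated if any adverse reaction to the study medication is noted". It sets no severity threshold and does not say what happens to the patient's data.

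Section 10(e) defines the term: "Patient participation is limited to the length of the hospitalization for breast reduction procedure plus the first postoperative visit". Section 10(f) places both primary endpoints inside that period: "Primary study endpoints are average VAS pain score during hospitalization and postoperative narcotic usage during the hospitalization". The surveys are completed at the first postoperative visit (section 10(g)).

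On the timing of treatment, section 10(g) says: "All subjects will receive perineural nerve block in the preoperative holding area prior to the case". The abstract and section 10(g) make clear that each breast is injected.

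On which arm carries the added risk, section 11 says: "Primary additional risk to subjects compared to the standardly practiced block is allergic or adverse reaction to the study medication posed by the administration of". The drug named at the end of that sentence is dexamethasone. Section 11 then lists its effects: "Adverse effects of this medication include behavioral disturbance, cardiac arrhythmia, hyperglycemia, and immune suppression". Only the experimental arm receives dexamethasone.

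On who knows the allocation, section 13 says: "Randomization status and all medications received will be disclosed to all healthcare personnel involved in the patient's care while in the hospital". Only the patient is blinded.

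Two other sections bear on the rule. Section 10(k) has the primary investigator evaluate adverse events related to study medication, with a MIDAS report for any adverse event and a summary to the IRB at 1 month if there are any. Section 10(l) withdraws subjects whose surgery departs from standard technique because of an intraoperative complication, and lets subjects withdraw at any time. No section provides for data collection after termination, an analysis of all randomised patients in their assigned group, or the handling of missing data.

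**The concern.** With a drug taken repeatedly, a rule like this can protect the patient by stopping exposure. Here the study treatment is complete, or nearly so, before the first postoperative score is recorded. What the rule ends is study follow-up.

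The patients affected are picked out by an event after randomisation that the protocol itself links to one arm. People who know the arm may also be the ones who decide whether a symptom is a reaction to study medication, and section 10(f) gives them no criteria. The number of patients terminated can therefore differ by arm for two reasons: a real difference in risk, and a difference in attribution.

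At stake is whether the groups compared on pain and opioid use are still the groups that were randomised. The later course of each reaction and the one-week surveys are also unprotected, in the patients for whom they matter most.

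**Working it through.** **1. What termination removes.** Participation (section 10(e)) runs from the hospital stay to the first visit. VAS and opioid use are measured in hospital and the surveys at the visit. The block precedes all of these. Termination on a reaction noted at any time after the block therefore ends study observation for whatever part of the primary and secondary outcomes is still to come.

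**2. The plan's own power figure.** Inputs from section 10(i): 30 per group, difference 1.5, SD 2.0, two-sided 0.05, two-group t-test.

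- Noncentrality = 1.5 / (2.0 × √(1/30 + 1/30)) = 2.905, with 58 degrees of freedom and critical t = 2.002.
- Power from the noncentral t distribution = 81.5%. The stated 81% reproduces.
- Section 10(d) anticipates about 60 subjects, which is 2 × 30, so there is no allowance for losses.

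**3. Shift in the VAS difference.** Let q be the share of the dexamethasone arm dropped entirely, and g the amount by which their mean VAS differs from that of the patients kept. The full arm mean is (retained mean) + q × g, so using only the retained patients shifts the arm mean by q × g. With no losses from control, that is also the shift in the group difference. The protocol gives neither q nor g, so the following are assumptions: 1 to 3 of 30 dropped, and g of 2 to 4 points in size.

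- Low end: (1/30) × 2 = 0.07 points; 0.067/1.5 = 4% of the design difference.
- High end: (3/30) × 4 = 0.40 points; 0.40/1.5 = 27%.

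The shift favours dexamethasone if those dropped would have had more pain than the rest, and control if they would have had less.

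**4. Chance of p<0.05 with no true effect.** This uses the same noncentral t calculation with the shift as the apparent difference and SD kept at 2.0.

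| Dropped (dexamethasone / control) | g | Shift | n compared (dexamethasone / control) | Chance of p<0.05 |
|---|---|---|---|---|
| 1 / 0 | 2 | 0.07 | 29 / 30 | 5.2% |
| 3 / 0 | 2 | 0.20 | 27 / 30 | 6.6% |
| 3 / 0 | 4 | 0.40 | 27 / 30 | 11.5% |
| 3 / 1 | 2 | 0.13 | 27 / 29 | 5.7% |

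In the last row, losses in control partly cancel: (3/30) × 2 − (1/30) × 2 = 0.13.

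**5. Power after losses.** For a true difference of 1.5 at 27 versus 30, the noncentrality is 1.5 / (2.0 × √(1/27 + 1/30)) = 2.827 with 55 degrees of freedom, and power is 79.3%. The loss against 81.5% is about 2 points, so selective removal is the larger concern.

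**The case against.** Five points can be made for the plan.

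- **The reaction is recorded.** A reader might infer that safety data are lost. The documents do not support that in general, because section 10(k) captures the triggering event. What remains unprotected is its later course, any other safety data, and the one-week visit.
- **Nothing says data are discarded.** Section 10(f) ends participation but does not delete scores already taken, and the mixed model over time in section 10(i) could use scores recorded before termination. Inpatient scores and medication records would also still exist in Epic (section 10(g)). This stands, and it makes complete removal the worst case. However, no section says that Epic data will be used after termination, and a patient terminated before the first postoperative score would contribute no VAS data. The t-test in the same section needs one average and one opioid total per patient, and values from a truncated stay are not comparable with complete ones.
- **The direction is unknown.** A reader might infer that patients in more pain leave the experimental arm and that dexamethasone will look better than it is. The effects listed in section 11 are not pain outcomes, and nothing in the protocol shows whether these patients would score higher or lower. This stands in full.
- **Triggers may be few and may occur in both arms.** Section 10(b) excludes patients allergic to study medications and those with diabetes. Both arms receive bupivacaine, and section 11 lists inadvertent systemic injection as a risk of the standard block. This stands as a reason not to attach a firm size to the problem.
- **The block is bilateral.** A reaction after the first side could precede the second, so the rule is not purely about data collection. This is true, but it covers only a short interval before surgery.

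**Conclusion.** The concern holds in a limited form. Read with section 10(e), the rule in section 10(f) ends study observation on a post-randomisation event that the protocol links mainly to one arm and that staff aware of the arm can attribute. Nothing in the plan secures the outcomes that follow. The comparison can be biased, in either direction.

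The size is illustrative. A shift of 0.07 to 0.40 points and a false-positive chance of about 5.2% to 11.5% rest on three assumptions: 1 to 3 of 30 dexamethasone patients dropped entirely, none from control, and a pain gap of 2 to 4 points. That gap is 1 to 2 of the plan's own standard deviations. Partial use of earlier scores or losses in both arms could make the effect smaller; a higher reaction rate would make it larger. The fall in power from 81.5% to 79.3% is minor.

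The documents do not support the stronger conclusions that all safety data are lost or that dexamethasone is bound to be favoured. The change is worth making because the rule is explicit and cheap to repair.

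**What to change.** Separate two things that section 10(f) now joins: stopping any study treatment still to be given, and ending data collection. The amended text should:

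1. State that after an adverse reaction, and likewise after a withdrawal for surgical complication under section 10(l), Epic pain scores, medication records, adverse events and the first-visit surveys continue to be collected unless the patient withdraws consent to data collection.
2. State in section 10(i) that all randomised patients are analysed in their assigned group.
3. Report reactions and terminations by arm.
4. Reconcile section 10(f) with the adverse event reporting in section 10(k) and the withdrawal provisions in section 10(l).

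This concerns data collection and analysis only; the clinical handling of a reaction is left to the sponsor.

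The cost is a few sentences in the protocol. The inpatient record is already the data source and the first visit is already scheduled. The one small burden is that the 4-hourly VAS and the surveys, which are requested for the study, continue for these patients.
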